5.5.1. Dose Modifications for Metformin

The major toxic effects of metformin which limit dose are gastrointestinal (nausea, abdominal bloating, diarrhea). During the ramp-up period, subjects experiencing gastrointestinal symptoms should be encouraged to take tablets with food. If no improvement, subjects should try taking study medication every other day for two weeks, once per day for two weeks and then twice per day thereafter. Subjects not tolerating study medication after this approach may go off study treatment but Investigators are urged to re-challenge willing subjects 4 weeks later. Dose adjustments, for reasons of toxicity, will be as in the tables below. (Please note that none of the recommended dose adjustments require splitting of study medication pills. Pills are not to be split or crushed, prior to taking, for any reason.) Breaks of up to 4 weeks consecutively or 8 weeks overall are allowed to ascertain the cause of the adverse events.

Gastrointestinal Toxicity Toxicity / Adverse Event	Grade	Investigator Action
Gastrointestinal Toxicity of any type	Grade 1	Patient should be encouraged to remain on full dose. If patient is unwilling, stop study treatment for one week. For subjects who were unwilling to remain on full dose, after one week without study drug, follow the ramp-up procedure. If Grade 1 symptoms persist or recur during the ramp-up or at full dose and the patient is unwilling to continue, follow instructions for Grade 2 toxicity.
Nausea Distension/Bloating Diarrhea Gastrointestinal - Other	Grade 2 (or higher)	Reduce to 500 mg BID for one week. If symptoms resolve or are Grade 1 only, after one week, resume full dose (1000 mg BID). If symptoms persist or recur at Grade 2 or higher, stop study treatment for 4 weeks, then resume study treatment as follows: Re-start study drug according to original ramp-up schedule. If toxicity persists or recurs, the study drug should be adjusted to the maximum dose that is tolerated with Grade 1 toxicity or lower. A second attempt to increase to full dose should be made 4 weeks later and if the full dose is not tolerated at that time, the maximum tolerated dose should be used for the remainder of the study.

15-1015

Hepatic dysfunction* (bilirubin > ULN except for Gilbert's Disease)	Grade 1 (or greater)	Hold study drug for up to 4 weeks. If bilirubin returns to normal within that time frame, begin 500 mg BID for 4 weeks, then 1000 mg BID.
Hepatic dysfunction* AST or ALT=1.8- 3.0 X ULN		Repeat AST & ALT in 2 weeks. If either AST or ALT > 1.8 X ULN, continue at discretion of Investigator, monitoring AST & ALT every two weeks until both < 1.8 X ULN – then resume annual testing. If Investigator decides to stop medication, resume once AST & ALT < 1.8 X ULN, starting with 500 mg BID for 4 weeks, then increasing to 2 tablets per day with annual AST & ALT assessments
Hepatic dysfunction* AST or ALT > 3.0 X ULN		Hold study drug. Repeat LFTs in 2 weeks. If AST and ALT < 1.8 ULN, resume medication. Resumption involves 500 mg BID for 4 weeks, then increase to 1000mg BID per day with resumption of protocol specified monitoring if both AST and ALT remain at < 1.8 x ULN. If repeat AST and ALT are 1.8-3.0 x ULN, follow steps as described in section above. If AST and/or ALT > 3.0 x ULN, initiate workup for liver disease. If AST or ALT=1.8-3.0 resume medication at the discretion of the investigator.
Renal dysfunction Creatinine > 115 µmol/L 1.3 mg/dL		Hold study drug for up to 4 weeks. After resolution of event, use ramp-up schedule.
Clinical diagnosis of congestive heart failure	> Grade 3	Hold study drug for up to 4 weeks. Re-start may be considered if underlying condition (e.g. acute MI) has resolved. If Metformin is started after CHF, the ramp-up schedule should be used. Do not re-start if symptoms persist or ongoing treatment of CHF is required.
Acidosis (Lactate > 5.0 mM) (pH < 7.3)	Grade 3	Stop study drug and do not re-start. Report as a serious adverse event.
Anemia Hgb < 110 or MCV > 105	> Grade 1	Perform CBC and serum B12 level. Initiate anemia workup if cause of anemia not apparent. Continue at full dose. (Treatment is not held for anemia regardless of toxicity grade.)
Skin Reactions Major – generalized urticaria, bullous rashes, exfoliative dermatitis	Generalized	Stop study drug and do not re-start

Stevens Johnson Syndrome Localized	Localized	Hold study drug for up to 4 weeks if possibly, probably or definitely related to study drug. When rash clears, 500 mg BID per day for 4 weeks, then 1000 mg BID per day – if rash recurs, and is thought to be possibly, probably or definitely related to study medication, discontinue study medication.
Hospitalization for any reason		Hold study drug for up to 4 weeks. The Investigator is to determine when it is safe to re-start. The drug should be re-started using a schedule (if the hospitalization resulted in discontinuation of the drug for 2 weeks or longer. If the discontinuation of the drug was less than 2 weeks, the drug should be re-started at full dose without a ramp-up.

* Be alert to signs of acidosis; protocol specific biochemistry should be checked annually. If subject develops malaise, nausea, dark urine, jaundice or right upper quadrant pain, study medication should be stopped until biochemistry is performed. Medication should be resumed according to the algorithms above (if first biochemistry results are normal, resume immediately at full dose)

Other Situations

Diagnostic Imaging:

If the subject is scheduled for any CT scans requiring intravenous contrast material, metformin should not be taken for 24 hours prior to the investigation or for 48 hours after the procedure. (This does not include contrast used for MRI or nuclear medicine scans, including MUGA). Study medication will then be resumed at full dose (without ramp-up) provided there is no concern about renal function. If there is concern about renal function, creatinine should be checked prior to resumption of study medication.

General Anesthetic:

If general anesthetic is required for surgery, study drug should not be taken on the morning of surgery or for 48 hours after anesthetic and surgery. Study medication will then be resumed at full dose (without ramp-up) provided there is no concern about renal function. The drug is restarted at full dose if the duration of interruption was less than 2 weeks. If the duration of drug interruption was more than 2 weeks, it should be restarted using a 4 week ramp-up schedule (one caplet per day for 4 weeks, then two caplets per day). If there is concern about renal function, creatinine should be checked prior to resumption of study medication.

Any Situation Considered Medically Necessary:

Study medication may be held in any situation which the Investigator considers it medically necessary, for up to 4 weeks.

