5.3.2 Treatment ARM B

Cycles 1 - 2: In order to minimize gastrointestinal discomfort, metformin dosing will be ramped up over a period of 2 weeks. Metformin treatment will

be started at 500 mg BID (Dose Level -2) and increased by an increment of 500 mg daily every week +/- 2 days provided no grade 2 or higher gastrointestinal toxicity is noted. If grade 2 or greater gastrointestinal toxicity occurs during the first 4 weeks of treatment, the subject will be evaluated every 2 weeks until resolution of toxicity to grade 0 or 1 and, then, the metformin dose will be increased to the next dose level. The target dose of metformin is 1000 mg BID. If patient cannot tolerate higher dose, metformin will continued at maximum tolerated dose as listed below.

Dose level	Metformin dose
Dose Level -2 (Week 1 +/- 2 days)	500 mg twice daily
Dose Level -1 (Week 2 +/- 2 days)	500 mg breakfast / 1000 mg at bedtime
Dose Level 0 (Week 3 and later)	1000 mg twice daily

Cycles 3 – 8: Continue metformin at maximum tolerated dose (up to 1000 mg BID). Start bicalutamide 50 mg/daily, orally, on a continuous basis to the end of study (week 32).

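### Metformin restart rules in 5.5.1 order full dose, or a return to 1000 mg BID, with no exception for an arm B man already fixed at a lower tolerated dose

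*Combined protocol and SAP*

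**What the plan says.** **Rules that hold a man at a lower dose.** Section 5.3.2 sets a target of 1000 mg BID for arm B but adds: "If patient cannot tolerate higher dose, metformin will continued at maximum tolerated dose as listed below". For Cycles 3–8 it continues the maximum tolerated dose, with 1000 mg BID as the ceiling. The Grade 2 gastrointestinal row of 5.5.1 describes a reduction, a hold and a repeat ramp-up. It then calls for one more try at the target after a further 4 weeks, and settles what follows a failure: "if the full dose is not tolerated at that time, the maximum tolerated dose should be used for the remainder of the study".

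**What full dose means.** The same row puts a number on it: "If symptoms resolve or are Grade 1 only, after one week, resume full dose (1000 mg BID".

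**Rules that restart at full dose.** There are four, all in 5.5.1, using the phrase five times:
- Diagnostic imaging (CT with intravenous contrast): "Study medication will then be resumed at full dose (without ramp-up) provided there is no concern about renal function".
- General anesthetic: the same sentence, followed by "The drug is restarted at full dose if the duration of interruption was less than 2 weeks".
- Hospitalization row: "If the discontinuation of the drug was less than 2 weeks, the drug should be re-started at full dose without a ramp-up".
- Footnote marked on the hepatic rows: "if first biochemistry results are normal, resume immediately at full dose".

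**Rows that name 1000 mg BID.** The bilirubin, AST/ALT > 3.0 x ULN and localized-skin rows restart at 500 mg BID for 4 weeks and then go to 1000 mg BID.

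**Related text.** Section 5.5 bans dose re-escalation outright. The anemia row says to stay on full dose.

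**The concern.** An arm B man can be fixed below 1000 mg BID in two ways: during the 5.3.2 ramp-up, or after a failed second attempt under the gastrointestinal row. If he then has a short interruption unrelated to tolerance, two instructions apply to him. One keeps the lower dose; the other restarts at full dose. A site following the restart rule to the letter re-exposes him to a dose already shown to be intolerable. A site following 5.3.2 or the gastrointestinal row does not. At stake are avoidable gastrointestinal toxicity in a few men and some inconsistency between sites in a trial that lists metformin safety and tolerability as a secondary endpoint.

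**Working it through.** The plan gives no figure on this point to reproduce. The check is a comparison of the rules, plus dose arithmetic and a rough count.

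**1. Can full dose mean the man's usual dose?** The gastrointestinal row attaches 1000 mg BID to the phrase and then contrasts it with the maximum tolerated dose. Within that row the two are different things, and 5.5.1 gives no other value for full dose.

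**2. What conditions does each restart rule carry?**

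| Rule in 5.5.1 | Restart dose | Condition stated | Exception for a fixed lower dose |
|---|---|---|---|
| Contrast CT | full dose | renal function | none |
| General anesthetic | full dose | renal function; under 2 weeks off | none |
| Hospitalization | full dose | under 2 weeks off; investigator decides when to restart | none |
| Hepatic-row footnote | full dose | first biochemistry normal | none |
| Bilirubin row | 500, then 1000 mg BID | bilirubin normal within 4 weeks | none |
| AST/ALT > 3.0 x ULN row | 500, then 1000 mg BID | AST and ALT below 1.8 x ULN | none |
| Localized-skin row | 500, then 1000 mg BID | rash clears and does not recur | none |

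Two further rules count tablets or caplets without giving a strength: the AST/ALT 1.8–3.0 x ULN row and the anesthetic rule for more than 2 weeks off. They do not clearly reach 1000 mg BID and are left out.

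**3. Dose step** (dose levels from 5.3.2).
- Level -2: 2 x 500 = 1000 mg/day.
- Level -1: 500 + 1000 = 1500 mg/day.
- Level 0: 2 x 1000 = 2000 mg/day.
- From Level -2: (2000 - 1000)/1000 = +100%.
- From Level -1: (2000 - 1500)/1500 = +33%.

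The scheduled ramp-up moves by 500 mg/day per week. Under the four full-dose rules the whole step is taken at once, after a hold as short as 24 h + 48 h = 3 days for a contrast CT. In the three named-dose rows it comes after 4 weeks at 500 mg BID.

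**4. How many men, under the four full-dose rules?** Let n be the number in arm B, f the fraction fixed below 1000 mg BID, and t the fraction of those with a qualifying short hold in 32 weeks. Men affected = n x f x t. Section 11.1 gives n = 44 in total, or 26 if the trial stops after the first cohort. The documents give neither f nor t; both are assumed at 0.05, 0.10 and 0.20.
- n = 44: 44 x 0.05 x 0.05 = 0.11; 44 x 0.10 x 0.10 = 0.44; 44 x 0.20 x 0.20 = 1.76.
- n = 26: 0.07; 0.26; 1.04.

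These are upper figures because they count the whole 32 weeks. A man fixed through the gastrointestinal row gets there later. If toxicity first appears on reaching Level -1 and returns there on restart, the path is 1 week ramp-up + 1 week reduced + 4 weeks off + 1 week ramp-up + 4 weeks to the second attempt = about 11 weeks. That leaves 21 of 32 weeks (0.656). Scaled by that factor, the results are 0.07 / 0.29 / 1.16 of 44 and 0.04 / 0.17 / 0.68 of 26. Men fixed during the 5.3.2 ramp-up lie nearer the unscaled figures. On-treatment CT is done only if clinically indicated (6.1, note 8), which also limits t.

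**The case against.** The strongest reply is that the documents already protect this man. The gastrointestinal row fixes his dose for the rest of the study, 5.3.2 does so through Cycle 8, and neither lapses after a scan or a short admission. A careful reader lets the specific provision govern. Other points support this:
- Three of the four rules use full dose mainly to say that no ramp-up is needed.
- The anemia row cannot mean that an anemic man on 500 mg BID should be raised to 1000 mg BID, so the table uses the phrase loosely.
- The footnote belongs to the hepatic rows and first sends the reader back to the algorithms above it.
- If toxicity recurs at Grade 2, the table reduces the dose again.

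Much of this stands, and it is why the point is small. It does not remove the conflict. No text says which rule prevails, and 1000 mg BID is the only value ever given for full dose. The footnote's parenthesis gives its own instruction when biochemistry is normal, without mentioning ramp-up. The three rows that name 1000 mg BID leave no room for a loose reading. The Grade 2 reduction acts only after toxicity has returned, and the same step points back to 1000 mg BID once symptoms settle. Nor can the 5.5 ban on re-escalation serve as the missing exception, because 5.5.1 itself orders re-escalation.

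A reader might infer that the ramp-up restarts (renal, heart failure, longer hospitalization) have the same fault. They do not: the 5.3.2 ramp-up advances only without Grade 2 or higher gastrointestinal toxicity and stops at the tolerated dose. It re-challenges a man but does not hold him at 1000 mg BID.

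**Conclusion.** The inconsistency is real and of low severity. Four full-dose restart rules and three rows naming 1000 mg BID conflict, on their wording, with the provisions that fix a lower maximum tolerated dose. The literal result is a rise of 33% or 100% in daily dose, to a level the man could not tolerate. The dose steps follow directly from 5.3.2. The count, probably one man or fewer, rests entirely on the assumed 5–20% rates and could differ if intolerance or short holds are more common.

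Two stronger inferences are not supported. A reader might suppose that men will in fact be over-dosed, but a careful site can reasonably keep the lower dose. A reader might also suppose that efficacy conclusions are affected, but nothing here alters power, type I error or the primary comparison. This is an inconsistency between dosing rules, not a questionable design choice.

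**What to change.** 1. Add one overriding sentence to 5.5.1: *Once a maximum tolerated dose has been fixed under 5.3.2 or the gastrointestinal row, 'full dose' and '1000 mg BID' in every restart or continuation rule of this section, including the anemia row, mean that dose.* A man whose second attempt under the gastrointestinal row is still due is not yet fixed by that row, so the attempt is preserved.
2. In 5.5, end the sentence banning re-escalation with *except as specified in 5.5.1*, so that the general rule and the table agree.

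With the overriding sentence in place, the individual restart rules need no rewording. The cost is one new sentence and one added clause in a protocol amendment. No visits, data or patients are added.

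### Section 5.5.1's metformin restart instructions mix mg doses with pill counts of unstated strength, overlap, and conflict with the bar on re-escalation, so the end dose after some restarts is not defined

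*Combined protocol and SAP*

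**What the plan says.** **Starting schedule (Section 5.3.2).** In Cycles 1-2, "metformin dosing will be ramped up over a period of 2 weeks". The dose begins at 500 mg BID and is "increased by an increment of 500 mg daily every week +/- 2 days". The text adds: "The target dose of metformin is 1000 mg BID". Section 9.1.8 repeats 1000 mg twice daily to the end of the study, and Section 5.4.3 has metformin taken twice daily.

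**Restarts (Section 5.5.1).**
- Persistent or recurrent gastrointestinal toxicity: the original ramp-up.
- Raised bilirubin and localized rash: 500 mg BID for 4 weeks, then 1000 mg BID.
- AST/ALT above 3.0 x ULN: "Resumption involves 500 mg BID for 4 weeks, then increase to 1000mg BID per day".
- AST/ALT 1.8-3.0 x ULN, if the investigator stopped the drug: "starting with 500 mg BID for 4 weeks, then increasing to 2 tablets per day with annual AST & ALT assessments".
- Renal dysfunction and heart failure: a ramp-up schedule, without saying which.
- Hospitalization with 2 weeks or more off drug: a schedule that is not named.
- General anaesthetic with more than 2 weeks off drug: "it should be restarted using a 4 week ramp-up schedule (one caplet per day for 4 weeks, then two caplets per day".

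**General rules.** Section 5.5 does not allow dose re-escalation. Section 5.5.1 forbids splitting pills and says that none of its adjustments needs it. Section 9.1.6 leaves metformin to commercial supply. No section states a tablet or caplet strength.

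**The concern.** Two neighbouring liver rows share the same first step, but one ends in mg and the other in a tablet count. The anaesthetic paragraph is written wholly in caplets. Because sites use commercial product of unstated strength, two sites can follow the same sentence and give different daily doses.

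Metformin is the only drug that separates the arms. What is at stake is uneven exposure in arm B (nominally 44 men), together with the ability to say, for a given restarted man, whether his dose was per protocol or a deviation.

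**Working it through.** **1. Reproduce the plan's own schedule.** 500 mg BID = 2 x 500 = 1000 mg/day. Adding 500 mg/day each week gives 1000, 1500 and 2000 mg/day in weeks 1, 2 and 3. This matches the Section 5.3.2 dose table, and 2 x 1000 = 2000 mg/day is the target.

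**2. Convert the pill-count rules to mg.** Let *s* be the strength in mg, which the documents do not give; 500 to 1000 is the assumed range. Both pill-count rules end at 2*s* mg/day. The share of target is 2*s*/2000. The step in the AST/ALT 1.8-3.0 row is 2*s* - 1000, because 500 mg BID is already 1000 mg/day.

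| *s* (assumed) | End dose, mg/day | Share of target | Step in AST/ALT 1.8-3.0 row |
|---|---|---|---|
| 500 | 1000 | 50% | 0 |
| 750 | 1500 | 75% | +500 |
| 850 | 1700 | 85% | +700 |
| 1000 | 2000 | 100% | +1000 |

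**3. Look for one strength that makes the liver row coherent.** Giving 500 mg BID without splitting needs a pill of 500 mg or less. With 500 mg pills the row's increase is zero. With 1000 mg pills alone, the 500 mg BID step cannot be given unsplit. The row works only if a site holds two strengths and takes the tablets in the last step to be the stronger one, which the text does not say.

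**4. Dose received over 12 weeks after a restart**, as a share of 12 weeks at 2000 mg/day (12 x 2000 = 24,000):
- Original ramp-up: (1000 + 1500 + 10 x 2000)/24,000 = 22,500/24,000 = 93.8%.
- 500 mg BID for 4 weeks, then 1000 mg BID: (4 x 1000 + 8 x 2000)/24,000 = 83.3%.
- Caplet rule: (4*s* + 8 x 2*s*)/24,000 = 20*s*/24,000, which is 41.7% at 500 mg and 83.3% at 1000 mg.

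**5. Set the rules side by side.**
- *Frequency.* Section 5.4.3 says twice daily; the caplet rule starts at once daily. The advice for gastrointestinal symptoms during ramp-up also leaves the twice-daily pattern (alternate days, then once daily, then twice daily) and gives no mg.
- *Overlap.* A surgical admission with more than 2 weeks off drug meets both the hospitalization row and the anaesthetic paragraph. The first names no schedule; the second uses caplets. Nothing says which governs.
- *Reference.* Only the gastrointestinal row points to the original ramp-up. The renal and heart-failure rows mention a ramp-up, while Section 5.3.2 and the anaesthetic paragraph each describe a different one. Section 9.1.8 refers to Section 5.4.3 for dose escalation, but that section contains no schedule.
- *Re-escalation.* Section 5.5 rules it out without exception, yet the restarts in Section 5.5.1 raise the dose in steps.

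**The case against.** **Different durations can be deliberate.** A reader might infer that 2 weeks in one place and 4 weeks in another is itself the contradiction. The documents do not support that. The 2-week ramp-up is the starting schedule, set to limit gastrointestinal discomfort. Three restart rows (bilirubin, AST/ALT above 3.0 x ULN, localized rash) share a 4-week step, and restarts may differ by event. This objection stands.

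**The target is still stated.** A reader might also infer that some men would never be directed back to full dose. Sections 5.3.2 and 9.1.8 keep 1000 mg BID as the target, and the word increasing in the AST/ALT 1.8-3.0 row argues against a reading in which nothing increases. The shortfall exists only in the restart text, and only for strengths below 1000 mg. This also stands, but it does not tell a site how many mg to give.

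**The caplet rule need not breach the no-splitting rule.** One whole 1000 mg caplet daily equals the 500 mg BID daily total, and two equal 2000 mg/day. At that strength the rule matches the daily totals of the three mg-based rows. The splitting difficulty therefore belongs to the 500 mg BID steps, not to the caplet rule.

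**The triggers are narrow and dosing is recorded.** The planned anaesthetic hold is the morning of surgery plus 48 hours, far short of 2 weeks. The tablet rule needs both AST/ALT of 1.8-3.0 x ULN and a decision to stop, and entry requires AST/ALT of at most 1.5 x ULN. Continuing below target at the maximum tolerated dose is already allowed. Pill diaries and source documents capture what was taken. All of this limits the size of the problem. Records show the dose taken, however, not which dose the protocol called for.

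**Conclusion.** The inconsistency is real and visible on the page: pill counts without a strength beside rows in mg, two rules for one surgical admission, ramp-up references that do not identify a schedule, and a bar on re-escalation that the restarts do not respect. These hold whatever the pill strength.

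The size of any dose shortfall is conditional. Both pill-count rules end at 50% of the 2000 mg/day target if pills are 500 mg, and at 100% if they are 1000 mg; both strengths are assumptions. The documents give no count of affected men. The narrow triggers suggest few. Alpha, power and sample size are built on proportions with undetectable PSA and do not change. This is an inconsistency in the instructions, worth correcting because it concerns the drug under test and is cheap to repair.

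**What to change.** The sponsor should reconcile Sections 5.3.2, 5.4.3, 5.5 and 5.5.1, and correct the pointer in Section 9.1.8:
- write every metformin step in mg and times per day, with no bare tablet or caplet counts;
- have each restart row name the schedule it means, including the renal, heart-failure and hospitalization rows;
- say which rule governs where the hospitalization row and the anaesthetic paragraph both apply;
- state how the bar on re-escalation relates to restarts that step the dose up.

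This does not require one ramp-up for every event. Which schedule and end dose apply to each event is for the sponsor to decide. The cost is table and paragraph wording in an amendment, with no change to the design or the analysis.
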